01/09/2023

[NCT ID not yet assigned] Unique Protocol ID: OZONE_EXO

OZONE_EXO: Comparative Analysis of Protocols for Dental Exactions in Patients at Risk of MRONJ: Case-control Study

Study Protocol

This study, entitled the OZOPROMAF protocol, was reviewed and approved by the Ethics Committee of University Hospital of Palermo, Policlinico P. Giaccone (approval number 01/2018).

Patients were consecutively enrolled from February 2018 to March 2020.

The study protocol conformed with the ethical guidelines of the 1964 Declaration of Helsinki and its later amendments or comparable ethical standards. All participants gave their written informed consent.

The aim of this study was to carry out a case-control study in order to compare two different protocols of dental extractions in patients at risk of MRONJ, with and without infiltration of a mixture of oxygen-ozone.

According to the considered criteria of inclusion and exclusion (Table 1), this study recruited 117 patients, 27 male and 90 female. Out of these patients, 54 had osteometabolic conditions, 57 were cancer patients, and 6 had both osteometabolic disease and cancer.

Table 1. Inclusion and exclusion criteria.

Inclusion criteria	
· age \geq 18 yrs· patients at risk of developing MRONJ for previous or current administration of drugs related· poor prognosis (for caries and/or periodontitis) of one or more teeth suitable for dental extraction
Exclusion criteria	
· previous radiation in the head and neck area· neoplastic involvement of the jaw· previous MRONJ diagnosis

The patients were randomly assigned to two groups using a simple randomization method. Specifically, a software program was used to arbitrarily select 38 patients (group Test) to receive ozone therapy by insufflation to the post-extraction site. The remaining 79 patients (group Control) did not receive this treatment.

During first consultation, medical, pharmacological, and dental history of patients were recorded, including age, sex, indications for use of MRONJ-related drugs, type and duration of MRONJ-related medication use, medical history of chemotherapy, concurrent use of other medications, other concomitant diseases, and smoking habits.

The patients recruited for the study (Table 2) were: "*onc1*" (cancer patients undergoing antiresorptive and/or anti-angiogenic therapies for medical indications), "*onc2*" (cancer patients taking antiresorptive treatments to manage osteometabolic disorders), and "*ost*" (non-oncologic patients taking antiresorptives for the treatment of osteometabolic conditions). So, based on type of drugs, route of administration and cumulative dose two risk categories were identified, namely low and high risk: *onc1* patients were generally considered to be at high risk; *onc2* and *ost* patients belonged to low-risk category.

Table 2. Descriptive data of enrolled patients.

	Test (N=38)	Controls (N=79)
Age		
Mean (SD)	66.7 (12.1)	69.6 (9.82)
Median [Q1, Q3]	71.00 [56.00, 74.75]	70.00 [63.00, 77.00]
Sex		
F	27 (71.1%)	63 (79.7%)
M	11 (28.9%)	16 (20.3%)
Patient risk category		
high	22 (57.9%)	35 (44.3%)
low	16 (42.1%)	44 (55.7%)
Patient type		
onc1	22 (57.9%)	35 (44.3%)
onc2	4 (10.5%)	2 (2.5%)
ost	12 (31.6%)	42 (53.2%)
Type of therapy		
antiresorptive medications	31 (81.6%)	74 (93.7%)
anti-angiogenetic medications	2 (5.3%)	1 (1.3%)
both	5 (13.2%)	4 (5.1%)

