On the day of the surgery (T0), the surgical protocol for Group B included the following steps: superficial local anesthesia using EMLA® cream, loco-regional anesthesia, incision and flap debridement, extraction of teeth with a poor prognosis, osteoplasty, achieving hemostasis, and suture.

Healing Evaluation and follow-up

In both groups, patients underwent additional follow-up visits at T1 (3-5 days), T2 (14 days), and T3 (6 weeks) post-extraction to meticulously monitor surgical wound healing by Inflammatory Proliferative Remodeling (IPR) Wound Healing Scale (Table 4) [20], and to record pain intensity by the NRS scale for enhanced ease of use, rather than the originally planned VAS scale [22].

The IPR scale provided a comprehensive assessment of wound healing through distinct subscales, each ranging from 0 to 1, resulting in a total score ranging from 0 to 16. These subscales evaluated the inflammatory response, proliferative response, and remodeling process. At the end of the follow-up period, the total IPR score was computed, with scores spanning from 0 to 16. Scores of 0-4 denoted poor healings, scores of 5-10 indicated acceptable healing, while scores of 11-16 suggested excellent healing.

Table 4. IPR (Inflammatory Proliferative Remodeling) Scale [21]

T/PHASE	Parameter	Score 0	Score 1	Total score
INFLAMMATORY T: 3-5 DAYS	Bleeding, spontaneously or on palpation	Yes	No	/8
	Granulation tissue	Yes	No	
	Haematoma	Yes	No	
	Tissue colour	Redder or whiter than opposite side tissue	Like the opposite side tissue	
	Incision margins	Incomplete flap closure/fibrin clot/partial necrosis/complete necrosis	Complete flap closure/fine fibrin line	

	Suppuration Edema NRS (1–10) Pain NRS (1–10)	Yes NRS 6–10 NRS 6–10	No NRS 1–5 NRS 1–5	
PROLIFERATIVE T: 14 DAYS	Re-epithelialisation	Partial	Complete	/5
	Tissue colour	Redder or whiter than opposite side tissue	Like the opposite side tissue	
	Scar	Scar wider than 2 mm/contour irregularity	No scar/scar less wide than 2 mm/contour regularity	
	Suppuration Pain NRS (1–10)	Yes NRS 6–10	No NRS 1–5	
REMODELING T: 6 WEEKS	Scar	Scar wider than 2 mm/contour irregularity	No scar/scar less wide than 2 mm/contour regularity	/3
	Tissue colour	Redder or whiter than opposite side tissue	Like the opposite side tissue	
	Pain NRS (1–10)	NRS 6–10	NRS 1–5	
TOTAL PROCESS				/16

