2.4 Statistical methods

The statistical analysis was performed using the R Statistical Software (v4.1.2; R Core Team 2021). Categorical variables were expressed as counts and percentages, quantitative variables as mean (standard deviation) or as median and interquartile range (the 25th and 75th percentiles), in case of skewed distributions. The Chi-square or the Fisher's exact test was used to compare groups A and B for categorical variables. Student's t test or the Wilcoxon-Mann-Whitney test was calculated to compare groups A and B for continuous variables. Statistically significant differences were assessed using two-sided P-values below 0.05.

At multivariable analysis, logistic regression was used to model binary responses (IPR>Median vs IPR≤Median) as related to demographic, pharmacological, systemic, and clinical covariates that have resulted significant at univariable analysis.

Table 4. IPR comparative statistical analysis

	Group T (ozone therapy) (N=38)	Group C (controls) (N=79)	P-value
Inflammatory T1 (3–5 Days)[§]			
Mean (SD)	2.00 (0.870)	2.49 (0.875)	0,006
Median [Q1, Q3]	2.00 [1.00, 2.75]	2.00 [2.00, 3.00]	
Proliferative T2 (14 Days)[§]			
Mean (SD)	4.24 (1.51)	3.70 (1.02)	<0.001
Median [Q1, Q3]	5.00 [4.00, 5.00]	4.00 [3.00, 4.00]	
Remodelling T3 (6 Weeks)[§]			
Mean (SD)	3.00 (0)	2.96 (0.192)	0,230
Median [Q1, Q3]	3.00 [3.00, 3.00]	3.00 [3.00, 3.00]	
IPR_Total Process[§]			
Mean (SD)	9.37 (1.79)	9.15 (1.38)	0,275
Median [Q1, Q3]	9.50 [9.00, 10.00]	9.00 [8.00, 10.00]	

[§]Wilcoxon signed-rang test

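### The study is labelled case-control although treatment is assigned and patients are followed forward, and the analysis guarantees no treatment effect adjusted for the protocol's own risk category

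*Combined protocol and SAP*

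**What the plan says.** The title and the aim both use the term case-control: "The aim of this study was to carry out a case-control study in order to compare two different protocols of dental extractions". The allocation paragraph on the same page says "The patients were randomly assigned to two groups using a simple randomization method"; software picked 38 patients for ozone and the other 79 became controls. Under Healing Evaluation and follow-up (section 2.3), "patients underwent additional follow-up visits at T1 (3-5 days), T2 (14 days), and T3 (6 weeks) post-extraction".

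The text before Table 2 states that "based on type of drugs, route of administration and cumulative dose two risk categories were identified": onc1 patients are high risk, onc2 and ost patients low risk. Table 2 gives the split by group.

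In section 2.4 the group comparisons are unadjusted: chi-square or Fisher for categorical variables, and for the rest Student's t or "the Wilcoxon-Mann-Whitney test was calculated to compare groups A and B for continuous variables". One multivariable analysis follows, in which "logistic regression was used to model binary responses" (IPR above the median or not) "as related to demographic, pharmacological, systemic, and clinical covariates that have resulted significant at univariable analysis". Neither treatment group nor risk category is named as a term that must be in the model.

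**The concern.** A case-control study selects people by outcome and looks back at exposure. A study that assigns treatment and looks forward is appraised by other criteria: how the allocation was generated and concealed, whether follow-up was complete, and whether the groups were comparable at the start. A reader who trusts the label will ask the wrong questions.

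The analysis gap is separate. The protocol defines a risk category from drug type, route and cumulative dose, and the two groups differ on it. The plan gives no assurance of a treatment estimate that takes it into account, and no IPR result is shown by risk category. A reader therefore cannot see how far the group differences depend on it. The one model that might have helped also discards information. Both group medians of total IPR (9.5 and 9) lie in the band where "scores of 5-10 indicated acceptable healing", so a median split falls inside one of the protocol's own healing categories.

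**Working it through.** **1. Label.** Title and aim: case-control. Allocation paragraph: assignment to ozone or no ozone. Section 2.3: treatment at T0, then visits at 3-5 days, 14 days and 6 weeks. The entry criteria in Table 1 contain no outcome. The last three agree with each other and not with the label.

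**2. Baseline risk (Table 2).** The printed shares reproduce: 22/38 = 57.9% and 35/79 = 44.3%. The difference is 0.579 - 0.443 = 0.136.
- Risk category, [22, 16] against [35, 44]: chi-square 1.90 on 1 df, P=0.17; Fisher P=0.24.
- Patient type, [22, 4, 12] against [35, 2, 42]: chi-square 6.76 on 2 df, P=0.034.

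**3. What the significance screen would do.** Section 2.4 does not say what the univariable analysis tests.
- If it means the between-group tests, risk category fails at 0.05 (P=0.17) and patient type, which contains it, passes (P=0.034).
- If it means association with IPR above the median, entry depends on power. With 57 high-risk and 60 low-risk patients and *assumed* rates of 30% against 40%, 45% or 50%, risk category passes about 20%, 39% or 60% of the time.
- Treatment is not assured entry either. Assume integer scores and R's default quartiles. The printed test median of 9.5 and Q1 of 9 then put 19 of 38 above 9, and the control median of 9 and Q3 of 10 allow 20 to 39 of 79 above 9. The pooled median is 9. The uncorrected chi-square P ranges from 0.008 (19/38 against 20/79) to 0.95 (against 39/79).

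**4. Internal check of the IPR results table (section 2.4).** Total IPR is the sum of the three subscores (8 + 5 + 3 = 16).
- Controls: 2.49 + 3.70 + 2.96 = 9.15, as printed.
- Test: 2.00 + 4.24 + 3.00 = 9.24, but 9.37 is printed.
- In points over 38 patients: 76 + 161 + 114 = 351 against 356. The gap is 0.13 per patient. Rounding four means to two decimals can produce at most 4 × 0.005 = 0.02.
- T3 in the test group is already at its maximum of 3. If all 38 patients contribute to every row, T1 or T2 is too low or the total is too high.
- The group difference in total IPR is 9.37 - 9.15 = 0.22 from the printed totals, but -0.49 + 0.54 + 0.04 = 0.09 from the subscores.

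**5. What adjustment could do.** If high-risk patients score g points lower than low-risk patients, the adjusted difference (test minus control) is roughly the unadjusted difference + 0.136 × g. For an *assumed* g of 0.5, 1 or 2 points the shift is 0.07, 0.14 or 0.27. The documents give no g. The shift is upward when high-risk patients heal worse: T2 (0.54 as printed) moves away from zero, and T1 (2.00 - 2.49 = -0.49 as printed) moves towards it.

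**6. Cost in precision.** For treatment and risk category, phi² = 1.90/117 = 0.016. The standard error factor is √(1/(1 - 0.016)) = 1.008, under 1%. For patient type, R² = 6.76/117 = 0.058, factor 1.030.

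**7. Allocation.** Under simple randomisation a 38:79 split has two-sided P=0.0002 for a 1:1 ratio and P=0.92 for 1:2 (39 expected). No intended ratio is stated.

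**The case against.** The label is a matter of wording: it changes no number, and the allocation paragraph tells the reader how the groups were formed. If allocation was random, unadjusted tests are valid and the risk imbalance is what chance produces. No document links the risk category to IPR. The covariate classes in section 2.4 are wide enough to include risk category or patient type, and the logistic results are not printed, so nothing shows that treatment or risk was left out. Any model added now is post hoc.

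All of this stands, and it limits the point. It does not remove the contradiction in the label, and it does not turn a model that may or may not contain treatment and risk into a planned adjusted estimate.

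Four stronger readings are tempting, and the documents do not support them.
- *The group differences are biased by risk.* No IPR result by risk is given, and the imbalance is compatible with chance.
- *T2 is fragile.* A Welch interval from the printed means and SDs runs from -0.002 to 1.08 (P=0.051) against the printed rank-test P<0.001. But this replaces the rank test behind the printed P-value with a mean comparison on a score near its ceiling, and it uses figures that may be wrong (step 4). Purely as an illustration, suppose one test-group T2 score of 5 had been entered as 0. The corrected mean would be 166/38 = 4.37 (SD 1.34), the difference 0.67 and the interval 0.18 to 1.16. Adjustment would also move T2 away from zero if high-risk patients heal worse.
- *The total-IPR result is safe unless the risk groups differ by 3.2 points.* That threshold (0.439/0.136) rests on the same disputed total.
- *The 38:79 split shows failed randomisation.* It fits 1:2, and if the number 38 was fixed beforehand the split says nothing.

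**Conclusion.** Two things hold. The case-control label contradicts the described design, and this needs no assumption. The plan also guarantees no treatment effect adjusted for risk category. That is narrower than saying adjustment is excluded, because whether treatment or risk category entered the logistic model cannot be told from the documents.

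The known size is a 13.6-point imbalance in high-risk patients, worth 0.136 points of group difference per IPR point between risk categories. The likely effect on the conclusions cannot be stated until Table 2's risk categories are linked to outcome and the test-group rows of the IPR table agree. The case for adjustment is precision and robustness. It should be made, but it does not undermine the unadjusted comparison if allocation was random.

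**What to change.** 1. In the title and aim, replace case-control with prospective parallel-group comparison. Reconcile this with the allocation paragraph: state whether allocation was randomised, the intended ratio, and when assignment was made.
2. Reconcile the test-group rows of the IPR results table (9.24 against 9.37), including the number of patients behind each row, before any further modelling.
3. Beside the planned tests, and labelled post hoc, report the treatment difference with 95% CI for total IPR, T1 and T2. Use a model of the undichotomised score with treatment and risk category both forced in, for example linear with robust standard errors. Check T2 with a proportional-odds model with the same two terms, because the test-group median and Q3 are both at the maximum of 5. T3 need not be modelled (test-group SD 0).
4. Optionally repeat with patient type as a sensitivity analysis, noting that onc2 has only 6 patients.

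The cost is a few words, one table check and a two-term model for three outcomes on data already collected. Correlation between treatment and risk category adds under 1% to the standard error (about 3% with patient type). The downside is a post hoc estimate and slightly more analysis.

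### The MRONJ risk category is a recode of patient type with no stated route or dose criterion, and adjusting for it would leave most of the between-arm difference in anti-angiogenic exposure in place

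*Combined protocol and SAP*

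**What the plan says.** In the combined protocol and SAP, the text above Table 2 defines three patient types:

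- onc1: "cancer patients undergoing antiresorptive and/or anti-angiogenic therapies for medical indications"
- onc2: "cancer patients taking antiresorptive treatments to manage osteometabolic disorders"
- ost: "non-oncologic patients taking antiresorptives for the treatment of osteometabolic conditions"

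It then states that "based on type of drugs, route of administration and cumulative dose two risk categories were identified, namely low and high risk". The allocation rule follows in the same sentence: onc1 "patients were generally considered to be at high risk", while onc2 and ost "patients belonged to low-risk category".

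Table 2 lists risk category, patient type and type of therapy by arm as three separate characteristics. It has no row for route, dose or duration. The opening Study Protocol section says that the history taken at first consultation included "type and duration of MRONJ-related medication use"; the items it names do not include route or dose.

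Section 2.4 plans a logistic model for a total IPR score above the median. Covariates come from several broad classes, one of them pharmacological, and enter only if significant in univariable analysis. It names neither risk category nor anti-angiogenic use, and it does not say that treatment group is kept in the model.

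**The concern.** A reader told that the category rests on drug type, route and cumulative dose will take the risk row of Table 2 as a check that drug exposure is balanced. The same reader will take any adjustment for risk as adjustment for exposure. If the category is only a relabelled patient type, neither inference follows. Patients in the high-risk group may differ in drug class and in time on treatment, and the category cannot register either.

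What is at stake is the ozone-versus-control comparison. Anti-angiogenic exposure is about three times as frequent in Test as in Control, and under the Section 2.4 rule nothing ensures that it enters the adjusted analysis.

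**Working it through.** **1. Reproduce the printed risk category (Table 2).**

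| | Test (N=38) | Control (N=79) |
|---|---|---|
| High, printed | 22 (57.9%) | 35 (44.3%) |
| onc1 | 22 | 35 |
| Low, printed | 16 (42.1%) | 44 (55.7%) |
| onc2 + ost | 4 + 12 = 16 | 2 + 42 = 44 |

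22/38 = 57.9% and 35/79 = 44.3%, as printed. The counts agree exactly in both arms.

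**2. Which split is it?** High/low totals are 22 + 35 = 57 and 16 + 44 = 60. Cancer status (onc1 + onc2 against ost) would give 57 + 6 = 63 and 12 + 42 = 54. The two differ by the six onc2 patients, who have cancer but are classed low. The category follows the indication for the drug, not whether the patient has cancer.

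**3. Anti-angiogenic exposure by arm (Table 2, alone plus both).**

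- Test: 2 + 5 = 7 of 38 = 18.4%
- Control: 1 + 4 = 5 of 79 = 6.3%
- Difference: 12.1 points (Wald 95% CI -1.4 to 25.5)
- Odds ratio: (7 × 74)/(31 × 5) = 518/155 = 3.3, exact 95% CI 0.83 to 14.3
- Fisher P=0.055; chi-square P=0.044 uncorrected, 0.090 with continuity correction
- Standardised mean difference: 0.37

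**4. Within the high-risk group.** Only the onc1 definition mentions anti-angiogenics. Assume that all 12 exposed patients are onc1; no cross-tabulation is given to confirm it.

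- Test 7/22 = 31.8%, Control 5/35 = 14.3%
- Odds ratio: (7 × 30)/(15 × 5) = 2.8 (2.7 by the conditional estimate, exact 95% CI 0.63 to 13.0), Fisher P=0.18

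**5. What adjustment for risk category would leave.** On the same assumption, weight both arms to the pooled high-risk share, 57/117 = 48.7%. Exposure becomes 0.318 × 0.487 = 15.5% in Test and 0.143 × 0.487 = 7.0% in Control. About 8.5 of the 12.1 points remain.

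**6. Would the factor pass the Section 2.4 screen?** Compare 12 exposed with 117 - 12 = 105 unexposed. The share above the median is not given by exposure. Splitting at strictly above the median puts at most half the patients in the upper group, so take 30% to 50% as an assumed range. By the normal approximation, the smallest observed difference significant at two-sided 0.05 is 1.96 × √[p(1-p)(1/12 + 1/105)].

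- p = 0.50: 1.96 × √(0.25 × 0.0929) = 0.30
- p = 0.30: 1.96 × √(0.21 × 0.0929) = 0.27

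A gap of roughly 27 to 30 percentage points in the outcome would be needed before the covariate was admitted.

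**The case against.** The strongest reply is that no stated analysis depends on the category. Allocation is described as simple randomization, Section 2.4 does not name risk category, and pharmacological covariates are already eligible for the model. The category concerns MRONJ risk while the analysed outcome is the IPR score, and the documents give no link from anti-angiogenic use to that score and no direction of bias. This stands as a limit: the harm is conditional. It does not answer the screening rule, which makes eligibility of little use for a factor with 12 exposed patients.

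Several stronger readings are tempting and are not supported:

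- **The category is a cancer/non-cancer split.** The six onc2 patients contradict this.
- **It carries no dose information.** The documents cannot show that. Indication may act as a proxy for route and dose, and the word generally suggests a group-level summary. They show only that no route or dose criterion is defined or reported.
- **Drug type plays no part.** If every anti-angiogenic user is onc1, all are classed high, so drug type is reflected, though incompletely.
- **Route and dose were not collected.** The history list is introduced as a set of inclusions and may not be complete.
- **The imbalance is hidden.** Type of therapy is printed in the same table, just below patient type.
- **Entering both variables would bias the result.** The high-risk term would be fully redundant with patient type. R drops the redundant coefficient, so the fit and the ozone estimate do not change.
- **The imbalance is statistically established.** The exact interval includes 1, and P runs from 0.044 to 0.090 by choice of test.

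**Conclusion.** The point holds in a limited form. As applied, the risk category is a two-level collapse of patient type, matching Table 2 exactly in both arms, and the stated route and cumulative-dose criteria cannot be found or reproduced from the document. It distinguishes oncologic from osteometabolic drug indication.

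Adjusting for it would not deal with the visible difference in anti-angiogenic exposure, 18.4% against 6.3%. Most of that difference would remain if all 12 exposed patients are onc1, which the definitions imply but no table confirms. Balance in duration of treatment cannot be judged, because duration was recorded but is not tabulated by arm.

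Confidence is high for the count match and modest for the consequence. The difference is a baseline feature worth adjusting for, and it is not evidence that the ozone comparison is biased in a known direction.

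**What to change.** In the Section 2.4 multivariable analysis, include treatment group and force in three baseline factors whatever their univariable significance:

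- drug indication, using either risk category or patient type but not both
- any anti-angiogenic use (yes/no)
- recorded duration of MRONJ-related medication

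Report the result as a declared adjusted comparison beside the unadjusted one. Outcome P-values are already printed in the IPR table, so the adjustment must be labelled post hoc and these covariates cannot be called prespecified.

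In the text above Table 2, describe the risk category as indication-based. If route and dose criteria were actually applied, state them instead.

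The cost is small, since the covariates come from data the protocol says were recorded. Beyond indication, the model spends one degree of freedom on anti-angiogenic use and one on duration if it is entered as a single linear term. With 12 exposed patients the anti-angiogenic coefficient will be imprecise, so its own estimate should not be interpreted. The high/low label also loses its claimed exposure basis.
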